# 8.3 Justification of Design

This trial employs an optimal Simon two-stage design with a= 0.05, assuming that the treatment is not worthy of further consideration if the probability of patients achieving a positive outcome (at least partial response and PFS 6 months) is less than 0.1. The design has 90% power if the true probability of positive outcome is 0.3 or greater. The stopping rule is designed to pause the trial if P(P[DLT > 0.3] > 0.7), using a beta-binomial model with a=1 and =4; that is, our prior expectation based on information equivalent to a total of five patients is that the P(DLT) = 0.2. The operating characteristics of the stopping rule, derived from a Monte Carlo simulation, are presented in the figure, where it is seen that, for instance, if the true probability of DLT is 0.3, the probability that the trial pauses is 0.4 and the expected number of participants accrued is 12.

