Number of Participants	Eighteen in the first stage and seventeen in the second stage, for a maximum of 35 patients
Investigational Product	lvosidenib, Nivolumab, route of administration: intravenous (IV) and oral (po), respectively
Estimated average treatment duration per patient	6 months
Duration of Participation	Up to 2 years
Reference therapies	Ivosidenib or Nivolumab
Statistical Methodology	An optimal Simon two-stage design is employed, where the primary endpoint is a composite of response (RANO for glioma patients or RECIST for solid tumor patients) and PFS6. Dose-limiting toxicity (DLT) is monitored throughout the trial using a Bayesian beta-binomial model. In secondary objectives, adverse events, response over time and progression-free survival are assessed. In exploratory objectives, the relationship between baseline biomarkers and response are described.
Safety Evaluations	Physical examination and ECOG performance status, vital signs, safety laboratory assessments (Hematology, chemistry, thyroid studies, pregnancy test (all women of child-bearing potential [WOCBP]) must have a negative pregnancy test to be eligible. Pregnancy testing to be done every $4 \pm 1$ weeks while on study treatment), AEs.
Data and Safety Monitoring Plan	Investigator/sub-investigators, regulatory, CRS management, clinical research coordinators, clinical research associates, data managers, and clinic staff meet regularly in disease center Data Safety Monitoring Boards (DSMB) to review and discuss study data to include, but not limited to, serious adverse events, participant safety issues, recruitment issues, accrual, protocol deviations, unanticipated problems, breaches of confidentiality Minutes of the disease center DSMB meetings are available to those who are unable to attend in person. A formal, sequential decision rule based on dose-limiting toxicity will be evaluated after every five participants have completed Cycle 1.

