# 7.5 Definition of DLT

AEs will be graded according to the NCI CTCAE version 5.0.

A DLT is defined as any AE (except clearly attributable to an extraneous cause, such as disease progression) occurring in Cycle 1 (only) that satisfies at least one of the following criteria:

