### 8.0 Statistical Analysis Plan and Sample Size Justification

The primary and secondary objectives and endpoints are in Section 2. The accrual goal for this trial is 35 participants evaluable for both safety and efficacy.

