### 8.1 Evaluability

### 8.1.1 Evaluability for Safety

Participants will be evaluable for safety if they receive a minimum of 75% of the first cycle of ivosidenib and have received one dose of nivolumab, unless they experience a DLT. The DLTwindow will be defined as from first dose through completion of the first 28-day cycle.

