### 8.2 Statistical Analysis Plan

# 8.2.1 Primary Objective: Efficacy

Given that the response rate would be expected to be< 10% and PFS < 3.5 months in this patient population of IDHI mutant advanced solid tumors or gliomas, we will consider a participant to have had a positive outcome if they have a positive PFS6 (PFS6 is scored as either No or Yes) *and* they have had at least a partial response (evaluated by RANO in glioma patients and RECIST in patients with solid tumors) at the 12 week scan.

An Optimal Simon two-stage design is employed, where a probability of positive outcome less than 0.1 would not be promising and a probability of positive outcome 0.3 would warrant further interest. In the first stage, 18 participants will be accrued. If three or more participants have positive outcomes, 17 more participants will be accrued. If 7 or more out of the 35 participants have positive outcomes, the null hypothesis p<0.1 will be rejected at a=0.05. This design has 90% power if p > 0.3.

For all tumor types, six-month progression-free survival (PFS6) is defined as survival to six months after the initiation of treatment without objective tumor progression

The probability of positive outcome and 95% confidence interval will be estimated using the method of Koyama and Chen (Koyama and Chen 2008).

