# 8.2.4 Exploratory Objective: Biomarkers and Response to Treatment

DLT (defined in Section 7.5) will be monitored throughout the trial and a stopping rule will be evaluated after every five participants have started Cycle 1. If the number of participants experiencing DLT equals or exceeds the number specified in the following table, the trial will be paused and the dosing reconsidered:

# Participants	# DLTs
5	3
10	5
15	7
20	8
25	10
30	12

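### The DLT stopping rule is read after five participants have started Cycle 1 in section 8.2.4 but after five have completed it in the Protocol Summary; separately, the expected accrual of 12 in 8.3 describes only trials that pause

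*Combined protocol and SAP*

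**What the plan says.** The plan gives two triggers for its only formal toxicity rule.

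- Section 8.2.4: "a stopping rule will be evaluated after every five participants have started Cycle 1". The table that follows pauses the trial at 3 DLTs in 5 participants, 5 in 10, 7 in 15, 8 in 20, 10 in 25 and 12 in 30.
- Protocol Summary, Data and Safety Monitoring Plan: the formal rule "based on dose-limiting toxicity will be evaluated after every five participants have completed Cycle 1".

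Section 8.1.1 says the DLT window "will be defined as from first dose through completion of the first 28-day cycle". Section 7.5 limits a DLT to an event "occurring in Cycle 1 (only) that satisfies at least one of the following criteria", yet its General list also counts a start of Cycle 2 delayed by more than two weeks for ivosidenib-related events.

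Section 8.3 derives the boundaries from a beta-binomial model with a Beta(1,4) prior, pausing when the posterior probability that the DLT rate exceeds 0.3 is above 0.7. It then states that at a true DLT rate of 0.3 "the probability that the trial pauses is 0.4 and the expected number of participants accrued is 12". Section 8.0 sets the size: "The accrual goal for this trial is 35 participants evaluable for both safety and efficacy".

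**The concern.** A participant who has just started Cycle 1 has contributed almost no DLT observation. Read at that moment, the table counts that participant as DLT-free, although the model behind the table takes all n outcomes as known. The formal rule could then miss or delay a pause that its boundaries call for. Nothing in the plan says which trigger governs, or what happens to a DLT that appears after a row has been read.

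The sentence in 8.3 raises a smaller matter. If only about 40% of trials pause and the rest can run to 35, a mean accrual of 12 over all trials is not possible under the DLT rule alone. A reader could wrongly take 12 as the trial's mean size at a 30% DLT rate.

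**Working it through.** **1. The boundaries reproduce and assume complete outcomes.** With x DLTs in n participants the posterior is Beta(1+x, 4+n−x). P(rate > 0.3) at the printed boundary, and with one DLT fewer:

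| n | boundary | at boundary | one fewer |
|---|---|---|---|
| 5 | 3 | 0.730 | 0.463 |
| 10 | 5 | 0.781 | 0.584 |
| 15 | 7 | 0.818 | 0.666 |
| 20 | 8 | 0.725 | 0.565 |
| 25 | 10 | 0.771 | 0.636 |
| 30 | 12 | 0.807 | 0.693 |

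Each printed count is the smallest that exceeds 0.7. The formula has no term for a participant whose window is still open.

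**2. The plan's own figures at a true DLT rate of 0.30.** An exact binomial recursion over the six looks, maximum 35, all windows observed and accrual held at each look, gives first-pause probabilities of 0.1631, 0.0618, 0.0322, 0.0733, 0.0237 and 0.0138.

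- P(pause) = their sum = 0.368, which rounds to the printed 0.4.
- Mean accrual among paused trials = (5×0.1631 + 10×0.0618 + 15×0.0322 + 20×0.0733 + 25×0.0237 + 30×0.0138) / 0.368 = 4.39 / 0.368 = 11.9, which matches the printed 12.
- Mean accrual over all trials = 4.39 + 0.632×35 = 26.5.

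At a DLT rate of 0.40 the same recursion gives P(pause) = 0.74.

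As a bound, if 40% of trials paused, all at the first look, and the rest reached 35, the mean would be 0.4×5 + 0.6×35 = 23. The Simon futility stop at 18 (section 8.2.1: "If three or more participants have positive outcomes, 17 more participants will be accrued") does not bring the mean to 12 either. With DLT independent of outcome, overall mean accrual is 15.3, 18.3, 23.5 and 25.8 at positive-outcome rates of 0, 0.1, 0.2 and 0.3. P(pause) rounds to 0.4 only at rates of about 0.24 or more, where the overall mean is at least 24.7.

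**3. Effect of when the look is taken.** The documents give no accrual pattern or DLT onset distribution, so these are assumptions: even starts 10.4 days apart (365/35, from the 12-month enrolment period), 20 or 30 days apart; onset uniform over 28 days; a DLT that appears after a look counts only at the next look. P(pause) from 200,000 simulated trials per cell, as ranges over the three spacings:

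| Look after the fifth start | DLT rate 0.30 | DLT rate 0.40 |
|---|---|---|
| same day | 0.23–0.29 | 0.60–0.67 |
| 7 days | 0.285–0.31 | 0.67–0.69 |
| 14 days | 0.32–0.33 | 0.70–0.71 |
| 28 days (all windows closed) | 0.37 | 0.74 |

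**4. If late DLTs go back to the row already reached.** The final count for each row is then the complete one, so P(pause) returns to 0.37 and 0.74. Only the date of the pause moves, by up to 28 days.

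**5. How the rows are filled also matters.** Suppose a row takes the first n participants who either complete the window or have a DLT, with accrual not held. Participants with a DLT qualify early while DLT-free participants wait 28 days, so rows fill preferentially with DLTs. At a DLT rate of 0.30 and 10.4-day spacing, P(pause) rises to about 0.41 with even starts and 0.45 with random arrivals, against 0.37. At 30-day even spacing the effect disappears. Counting in enrolment order avoids it at any spacing.

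**The case against.** The strongest reply is that the loss in pause probability needs two things section 8.2.4 does not state: a look on the very day of the fifth start, and late DLTs ignored until the next look. The section says DLT is monitored throughout, section 7.5 has safety data reviewed continuously, and section 9.4 lets the disease-center DSMB and the DSMC suspend accrual. That stands. A reader might infer that the rule as written has definitely lost power; the documents do not support this, because a late DLT may be applied to the row already reached. What remains is that the plan does not say so, and its two triggers conflict.

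A reader might also find a third look time in section 8.1.1: "Participants will be evaluable for safety if they receive a minimum of 75% of the first cycle of ivosidenib". That is a minimum-exposure criterion for evaluability, not a time for reading the table, and the same section closes the DLT window at the end of the 28-day cycle.

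On accrual, a reader might conclude that the simulation or a boundary is wrong. Neither is: 0.4 and 12 both reproduce once 12 is read as conditional on a pause. The figure cited in 8.3 is not shown in the available text and may already carry that label; the sentence does not.

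**Conclusion.** The conflict between section 8.2.4 and the Protocol Summary is real and nothing else in the plan resolves it. It should be fixed because it concerns the timing of the formal toxicity rule.

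Its size depends on the reading. In the literal worst case, P(pause) falls by 0.08 to 0.14 at a DLT rate of 0.30 (0.37 to 0.29–0.23) and by 0.07 to 0.14 at 0.40 (0.74 to 0.67–0.60), given the spacing and onset assumptions above. In the mildest reading nothing is lost except up to 28 days. Ongoing review and the power to suspend accrual limit the consequence in either case.

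The accrual sentence is a minor point, a missing qualifier. No boundary and no pause probability changes.

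**What to change.** 1. Reconcile section 8.2.4 with the Protocol Summary. Row n should count the first n safety-evaluable participants in enrolment order. It should be read once all n DLT windows have closed, or earlier if the DLTs among those n already reach the boundary. Do not fill rows with whoever first completes the window or has a DLT, unless accrual is held at each look.
2. Reconcile the Cycle 2 delay criterion in section 7.5 with the restriction to Cycle 1 and with the 28-day window in 8.1.1, since a delay beyond two weeks cannot be known on day 28.
3. In 8.3, say that at a true DLT rate of 0.3 the chance of a pause is about 0.4 (0.37) and that trials which pause have accrued about 12 on average. If an overall mean is given, label it: 26.5 of 35 for the DLT rule alone, with accrual held at each look and no futility stop. With the futility stop it is lower, about 18 at a positive-outcome rate of 0.1 and 26 at 0.3, if DLT and outcome are independent.

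The edit is a few sentences. The operational cost is that a look without an early crossing comes up to about 28 days later than under the *started* wording. If accrual is not held, about 2 more participants start in that time at 10.4-day spacing (28/10.4 = 2.7, so two full intervals), 1 at 20 days and none at 30 days. If the Cycle 2 delay criterion is kept and awaited, the delay is up to 42 days, with up to 4 more starts at 10.4-day spacing.

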### 9.0 Study Management, Agreement, and Ethical Considerations

### 9.1 IRB Approval and Consent

It is expected that the IRB will have the proper representation and function in accordance with federally mandated regulations. The IRB should approve the consent form and protocol.

In obtaining and documenting informed consent, the investigator should comply with the applicable regulatory requirement(s) and should adhere to Good Clinical Practice (GCP) and to ethical principles that have their origin in the Declaration of Helsinki.

Before recruitment and enrollment onto this study, the patient will be given a full explanation of the study and will be given the opportunity to review the consent form. Each consent form must include all the relevant elements currently required by the FDA Regulations and local or state regulations. Once this essential information has been provided to the patient and the investigator is assured that the patient understands the implications of participating in the study, the patient will be asked to give consent to participate in the study by signing an IRB approved consent form.

Prior to a patient's participation in the trial, the written informed consent form should be signed and personally dated by the patient and by the person who conducted the informed consent discussion.

# 9.2 FDA Approval

This study will be conducted under an IND held by [name] at the UPMC Hillman Cancer Center, which will be responsible for facilitating all communications with the FDA on behalf of the IND holder.

#### 9.3 Required Documentation

Prior to the commencement the study the UPMC Hillman Cancer Center audit and trial oversight processes must be reviewed and approved by the Protocol Review and Monitoring System or Protocol Review Committee (PRMS/PRC).

Before the study can be initiated, the following documentation must be provided to PRMS/PRC at the UPMC Hillman Cancer Center:

- A copy of the official IRB approval letter for the protocol and informed consent
- IRB membership list
- CVs and medical licensure for the PI and any sub-investigators who will be involved in the

study.

- Form FDA 1572 appropriately filled out and signed with appropriate documentation
- CAP and CLIA Laboratory certification numbers and institution lab normal values
- Financial disclosure forms for the PI and any sub-investigators who will be involved in the study
- Investigational drug accountability standard operating procedures

Additionally, before the study can be initiated, the required executed research contract/subcontract must be on file with the UPMC Hillman Cancer Center. Once all required documents are received, reviewed and approved by the Coordinating Center's designated representative(s), a patient may be enrolled.

# 9.4 Data and Safety Monitoring Plan

Investigators, Sub-investigators and clinical research staff meet regularly in disease center Data Safety Monitoring Boards (DSMB) to review and discuss study data to include, but not limited to, the following:

- Serious adverse events
- Subject safety issues
- Recruitment issues
- Accrual
- Protocol deviations
- Unanticipated Problems
- Breaches of confidentiality

Minutes from the disease center DSMB meetings are available to those who are unable to attend in person or participate via teleconference.

All toxicities encountered during the study will be evaluated on an ongoing basis according to the NCI Common Toxicity Criteria Version 5.0. All study treatment associated adverse events that are serious, at least possibly related and unexpected will be reported to the IRB. Any modifications necessary to ensure subject safety and decisions to continue or close the trial to accrual are also discussed during these meetings. If any literature becomes available which changes the risk/benefit ratio or suggests that conducting the trial is no longer ethical, the IRB will be notified in the form of an Unanticipated Problem submission and the study may be terminated.

All study data reviewed and discussed during these meetings will be kept confidential. Any breach in subject confidentiality will be reported to the IRB in the form of an Unanticipated Problem submission. The summaries of these meetings are forwarded to the UPMC Hillman Cancer Center DSMC which also meets monthly following a designated format.

For all research protocols, there will be a commitment to comply with the IRB's policies for reporting unanticipated problems involving risk to subjects or others (including adverse events). DSMC progress reports, to include a summary of all serious adverse events and modifications, and approval will be submitted to the IRB at the time of renewal.

Protocols with subjects in long-term (survival) follow-up or protocols in data analysis only, will be

reviewed bi-annually.

Both the UPMC Hillman Cancer Center DSMC as well as the individual disease center DSMB have the authority to suspend accrual or further investigate treatment on any trial based on information discussed at these meetings.

All records related to this research study will be stored in a locked environment. Only the researchers affiliated with the research study and their staff will have access to the research records.

# 9.5 Amendments to the Protocol

All modifications to the protocol, consent form, or questionnaires will be submitted to the University of Pittsburgh IRB (Pitt IRB) for review and approval. A list of the proposed modifications or amendments to the protocol and/or an explanation of the need of these modifications will be submitted, along with a revised protocol incorporating the modifications. Only the Study Lead PI can authorize any modifications, amendments, or termination of the protocol. Once a protocol amendment has been approved by the Pitt IRB, the Regulatory Specialist will send the amended protocol and consent form (if applicable) to the affiliate institutions electronically. Upon receipt of the packet the affiliate institution is expected to do the following:

- The affiliate must reply to the email from the Regulatory Specialist indicating that the amendment was received by the institution and that it will be submitted to the local IRB.
- The amendment should be submitted to the affiliate institution's IRB as soon as possible after receipt. The amendment **must** be IRB approved by the institution **within 3 months** from the date that it was received.
- The UPMC Hillman Cancer Center version date, amendment number, or both must appear on the affiliate consent form and the affiliate IRB approval letter. The version dates can be found on the footer of every page of the protocol and consent form. The amendment number can be found on the University of Pittsburgh IRB (Pitt IRB) amendment approval letter that is sent with the protocol/amendment mailing.

The IRB approval for the amendment and the amended consent form (if amended consent is necessary) for the affiliate institution must be sent to the designated CRS Regulatory Specialist as soon as it is received.

# 9.6 Annual IRB Renewals, Continuing Review, and Final Reports

A continuing review of the protocol will be completed by the Pitt IRB and the participating institutions' IRBs at least once a year for the duration of the study. The annual IRB renewal approvals for participating institutions should be forwarded promptly to the Regulatory Specialist. If the institution's IRB requires a new version of the consent form with the annual renewal, the consent form should be included with the renewal letter.

# 9.7 Record Retention

Study documentation includes all CRFs, data correction forms or queries, source documents, Sponsor-Investigator correspondence, monitoring logs/letters, and regulatory documents (e.g., protocol and amendments, IRB correspondence and approval, signed patient consent forms).

Source documents include all recordings of observations or notations of clinical activities and all reports and records necessary for the evaluation and reconstruction of the clinical research study.

Government agency regulations and directives require that all study documentation pertaining to the conduct of a clinical trial must be retained by the study investigator. In the case of a study with a drug seeking regulatory approval and marketing, these documents shall be retained for at least two years after the last approval of marketing application in an International Conference on Harmonization (ICH) region. In all other cases, study documents should be kept on file until three years after the completion and final study report of this investigational study.

### 9.8 Obligations of Study Site Investigators

The PI is responsible for the conduct of the clinical trial in accordance with Title 21 of the Code of Federal Regulations and/or the Declaration of Helsinki. The Study PI is responsible for personally overseeing the treatment of all study patients. He/she must assure that all study site personnel, including sub-investigators and other study staff members, adhere to the study protocol and all FDA/GCP/NCI regulations and guidelines regarding clinical trials both during and after study completion.

The Study Site PI will be responsible for assuring that all the required data will be collected and entered into the CRFs. Periodically, monitoring visits or audits will be conducted and he/she must provide access to original records to permit verification of proper entry of data.

